3.2.1.2. Time to PSA Progression

Time to PSA progression is defined as the time in months from randomization to the date of the first PSA value demonstrating progression, while patients are on study treatment, which is subsequently confirmed at least 3 weeks later.

For patients who do not have treatment suspended due to undetectable PSA at week 36: those with PSA decline at week 25, the PSA progression date is defined as the date that a $\geq 25\%$ increase and an absolute increase of $\geq 2 \mu g/L$ (2 ng/mL) above the nadir (or baseline for patients with no PSA decline by week 25), which is subsequently confirmed at least 3 weeks later.

For patients who have treatment suspended due to undetectable PSA at week 36: following treatment suspension and reinitiation of study drug, the PSA progression date is defined as the date that a \geq 25% increase and an absolute increase of \geq 2 µg/L (2 ng/mL) above the nadir (re-baselined after week 36), which is confirmed by a second consecutive value obtained at a subsequent study visit at least 3 weeks later. PSA re-baseline value is defined as the last PSA assessment prior to or on the date of reinitiation. The nadir for these patients, is defined as minimum PSA value at the PSA re-baseline value visit and subsequent visits. Refer to Section 6.2.2 for details on censoring rules.

3.2.1.3. Time to First Use of New Antineoplastic Therapy

Time to first use of new antineoplastic therapy is defined as the time in months from randomization to first use of new antineoplastic therapy for prostate cancer. This will include medications used specifically for prostate cancer treatment including cytotoxic chemotherapy, abiraterone acetate, hormonal agents, prostate cancer vaccines, or nonradioactive bone-targeting agents and systemic radiopharmaceuticals for prostate cancer. Medications will be recorded on the 'Long Term Follow-up Antineoplastic Therapies' CRF page. Patients not starting treatment with a new antineoplastic therapy at the time of analysis will be censored at the date of last assessment before the analysis data cutoff date.

3.2.1.4. Overall Survival

Overall survival is defined as the time in months between randomization and death due to any cause. Refer to Section 6.2.4 for details on censoring rules.

Analysis	Endpoint	Additional
		notes
Other Seconda	ry Endpoints	
Efficacy	 The 2 comparisons (Enzalutamide in combination with leuprolide versus placebo in combination with leuprolide, Enzalutamide monotherapy versus placebo in combination with leuprolide) will be carried out for all other secondary endpoints: Time to distant metastasis 	See Section 6.3
	 Proportion of patients per group who remain treatment-free 2 years after suspension of study treatment at week 37 due to undetectable PSA Proportion of patients per group with undetectable PSA 2 years after suspension of study treatment at week 37 due to undetectable PSA Proportion of patients per group with undetectable PSA at 36 weeks on study drug Time to resumption of any hormonal therapy following suspension at week 37 due to undetectable PSA Time to castration resistance Time to symptomatic progression 	
DDO	Time to first symptomatic skeletal event	9
PKO	 Time to clinically relevant pain progression defined as time in months from randomization to the time a 2-point increase from baseline on the BPI-SF question 3. Time to functional status decline (deterioration) defined as the time in months from randomization to the time of a 10-point decline (deterioration) in global FACTP score from baseline. Pain by BPI-SF and QoL by FACT-P, EQ-5D-5L and QLQ-PR25 questionnaires Additional PRO endpoints can be found in a separate SAP specific to PROs 	Section 6.4

3.2.2. Other Secondary Endpoints

3.2.2.1. Time to distant metastasis

The time to distant metastasis is defined as the time in months from randomization to the earliest objective evidence of distant soft tissue metastases or metastatic bone disease by BICR. Soft tissue disease including lymph nodes above the aortic bifurcation and outside the pelvis and any bone metastases will be counted as distant metastases. Refer to Section 6.3.1 for details on censoring rules.

3.2.2.2. Proportion of patients who remain treatment-free 2 years after suspension of study treatment at week 37 due to undetectable PSA

The proportion of patients who remain treatment-free 2 years after suspension of study treatment at week 37 due to undetectable PSA is defined as number of patients remaining treatment-free 2 years after suspension of study treatment at week 37 due to undetectable PSA divided by the total number of patients with suspension of study drugs at week 37 due to undetectable PSA in each treatment group.

3.2.2.3. Proportion of patients per group with undetectable PSA 2 years after suspension of study treatments at week 37 due to undetectable PSA

The proportion of patients per group with undetectable PSA 2 years after suspension of study treatments at week 37 due to undetectable PSA is defined as number of patients with undetectable PSA 2 years after suspension of study treatments at week 37 due to undetectable PSA divided by the total number of patients with suspension of study drugs at week 37 due to undetectable PSA in each treatment groups.

3.2.2.4. Proportion of patients per group with undetectable PSA at 36 weeks on study drug

The proportion of patients per group with undetectable PSA at 36 weeks on study drug is defined asby the number of patients with undetectable PSA at 36 weeks divided by the total number of patients with PSA value at week 36 in each treatment group.

3.2.2.5. Time to resumption of any hormonal therapy following suspension at week 37 due to undetectable PSA

The time to resumption of any hormonal therapy following suspension at week 37 due to undetectable PSA is defined as the time in months between the date of treatment suspension at week 37 due to undetectable PSA and the date that hormonal therapy is restarted. Patients not starting hormonal therapy at the time of analysis will be censored at the date of last assessment before the analysis data cutoff date.

3.2.2.6. Time to castration resistance

Time to castration resistance applies only to patients receiving leuprolide treatment and is defined as the time in months from randomization to the first occurrence of radiographic disease progression by BICR, PSA progression (as defined above in Section 3.2.1) or symptomatic skeletal event whichever occurs first with castrate levels of testosterone (<50 ng/dL). The latest testosterone value measured prior to or at the date of radiographic disease progression by BICR, PSA progression or a symptomatic skeletal event is used to

determine if the event is a castration resistance event. Refer to Section 6.3.6 for details on censoring rules.

3.2.2.7. Time to symptomatic progression

Time to symptomatic progression is defined as the time in months from randomization to development of a skeletal-related event, worsening of disease-related symptoms requiring initiation of a new antineoplastic therapy, or development of adverse events and clinically significant signs and/or symptoms due to loco-regional tumor progression requiring opiate use, surgical intervention or radiation therapy, whichever occurs first. Refer to Section 6.3.7 for details on censoring rules.

3.2.2.8. Time to first symptomatic skeletal event

Time to first symptomatic skeletal event is defined as the time in months from randomization to use of radiation therapy (external beam radiation therapy or radionuclides) or surgery to bone for prostate cancer, findings of clinically apparent pathologic bone fracture or of spinal cord compression, or new use of opiate and/or systemic antineoplastic therapy due to bone pain collected in the SSE CRF, whichever occurs first. Because skeletal events are expected to occur after radiographic progression, the analysis of time to first symptomatic skeletal event will be performed with the final overall survival analysis. Refer to Section 6.3.8 for details on censoring rules.

3.2.2.9. Patient-Reported Outcomes (PRO)

The assessment of pain progression will be conducted using the BPI-SF (Cleeland 2006, Cleeland 2009) that has been subject to extensive validation processes. This questionnaire uses a self-reported scale assessing level of pain, its effect on activities of daily living, and analgesic medication use.

This study will use the short form containing 9 main questions related to pain and analgesic medication use. The primary question (paraphrased) is "On a scale of 0 to 10, please rate your pain at its worst in the last 24 hours."

Time to clinically relevant pain progression is defined as the time in months from randomization to onset of pain progression, where pain progression is defined as a 2-point or more increase from baseline in the question 3 score.

Additional pain analyses with further details about questionnaires and associated derived variables can be found in a separate SAP specific to PROs.

Patient-Reported Outcomes (PRO) - Quality of Life Quality of life will be assessed by FACT-PEQ5D-5L and QLQ-PR25 questionnaires.

The FACT-P (Cella et al. 1993, Esper et al. 1997, 1999) is a multidimensional, self-reported, quality of life instrument specifically designed for use with prostate cancer patients. It consists of 27 core items that assess patient function in 4 domains: Physical, Social/Famil y, Emotional, and Functional wellbeing, which is further supplemented by 12 site-specific items to assess prostate cancer related symptoms. Each item is rated on a 0 to 4 Likert-type scale,

and then combined to produce subscale scores for each domain, as well as a global quality of life score with higher scores representing better quality of life.

Time to functional status deterioration will be assessed and is defined as the time in months from randomization to the time of a 10-point decline (deterioration) in global FACT-P score. The FACT-P domain scores and global score will be calculated using the Manual of Functional Assessment of Chronic Illness Therapy (FACIT) Measurement System (Cella, 1997).

The EQ-5D-5L questionnaire (Herdman et al. 2011, Janssen et al. 2013) is a standardized instrument for use as a measure of health-related quality and general health status. With the EQ-5D-5L questionnaire, patients will self-rate their current state of mobility, selfcare, , pain/discomfort, and anxiety/depression on a 5point categorical scale ranging from "no problem" to "extreme problem" within each dimension and EQ-VAS.

The European Organization for Research and Treatment of Cancer (EORTC) QLQ-PR25 (Van Andel et al. 2008), a module of the EORTC QLQ30 questionnaire, was developed to assess the quality of life of patients with prostate cancer. Patients will self-rate their current state of pain as it relates to urination, ease and frequency of urination, and bowel and other problems during the past week. Patients will also answer 5 questions about weight loss/gain and sexual interest and 4 questions about sexual activity during the past 4 weeks. Patients will choose 1 of 4 possible responses that record level of intensity (not at all, a little, quite a bit, very much) within each dimension.

Additional QoL analyses with further details about questionnaires and associated derived variables can be found in a separate SAP specific to PROs.

Analysis	Endpoint	Additional notes
Exploratory E	ndpoints	
Efficacy	• PFS2 will be assessed for the 2 comparisons (Enzalutamide in combination with leuprolide versus placebo in combination with leuprolide, Enzalutamide monotherapy versus placebo in combination with leuprolide).	See Section 3.3.1

3.3. Exploratory Endpoint(s)

3.3.1. Progression-free survival on first subsequent therapy

Progression-free survival on first subsequent therapy (PFS2) is defined as the time in months from date of randomization to date of investigator-determined disease progression (PSA progression, progression on imaging, or clinical progression) or death due to any cause, whichever occurs first, while the patient was receiving first subsequent therapy for prostate cancer. For censoring rules see Section 6.5.

3.4. Baseline Variables

3.4.1. Study Drug, Study Treatment, and Baseline Definitions

The date of first dose (start date) of study treatment in the combination arms is the earliest date of non-zero dosing for each of the study drugs (enzalutamide/placebo or leuprolide).

The date of first dose (start date) of study treatment in the enzalutamide monotherapy arm is the earliest date of non-zero dosing of enzalutamide.

The date of last dose of study treatment in the combination arms is the latest date of non-zero dosing for each of the study drugs.

The date of last dose of study treatment in the enzalutamide monotherapy arm is the latest date of non-zero dosing of enzalutamide.

Definition of Baseline:

No windowing will be applied when defining baseline. For example, the protocol requires safety assessments to be performed within 28 days prior to randomization; however, values outside this window will not be excluded when determining baseline assessments. Any deviations from the protocol specified window will be documented as protocol deviations.

Definition of baseline for efficacy and baseline analyses

The last measurement prior to randomization will serve as the baseline measurement for efficacy and baseline analyses.

Definition of baseline for PRO

Per protocol, the first PRO assessment is planned to occur prior to dosing on Day 1; therefore, the last measurement on or prior to the day of first dose of study treatment (on or prior to randomization for patients randomized but not dosed) will be used as the baseline measurement.

Definition of baseline for safety analyses

The last available assessment on or prior to the date of first dose of study treatment (or prior to randomization for patients randomized but not dosed) is defined as the 'baseline' value or 'baseline' assessment for safety analyses. If an assessment is planned to be performed prior to the first dose of study treatment in the protocol and the assessment is performed on the same day as the first dose of study treatment, it will be assumed that it was performed prior to study treatment administration, if assessment time is not collected or is missing. If assessment times are collected, the observed time point will be used to determine pre-dose on study Day 1 for baseline calculation (this only applies for safety). Unscheduled assessments will be used in the determination of baseline.

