6.3.3. Directions for Administration of Leuprolide

Leuprolide acetate for administration as a 22.5 mg injection once every 12 weeks formulated for either intramuscular or subcutaneous injection is allowed. Three injections will provide 36 weeks of treatment.

The leuprolide acetate formulation for intramuscular injection is supplied as sterile lyophilized microspheres along with an accompanying diluent. The microspheres are to be reconstituted as described in the prescribing information and administered as a single intramuscular injection of 22.5 mg once every 12 weeks.

The leuprolide acetate formulation for subcutaneous injection is supplied as sterile powder along with an accompanying liquid gel solution. The powder is to be mixed with the liquid as described in the prescribing information and administered in clinic by study site personnel as a single subcutaneous injection of 22.5 mg once every 12 weeks.

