18.1. Rationale and Treatment Plan

Primary endpoint analyses demonstrated that the primary efficacy endpoint of metastasis free survival (MFS) was established and the safety profile of enzalutamide was confirmed, therefore, the treatment codes for all patients will be unblinded and an open-label treatment period is being implemented. The final analysis of the key secondary endpoint for overall survival (OS) will be performed as planned. Patients will continue to receive their originally assigned study treatment in this open-label (OL) study period. Patients assigned to the placebo plus leuprolide arm will no longer take the placebo capsules. No crossover treatment will be implemented.

For patients whose cancer has not progressed radiographically, locally (change was effective as of 31-Mar-2023) performed scans (CT/MRI and bone scan) will be conducted until the patient's cancer progresses radiographically. Scans read centrally by blinded independent central reviewer (BICR) ceased as of 31-Mar-2023. Prostate-specific antigen (PSA) levels will also be done at a local lab and monitored by the investigator per standard of care (SOC) effective date of 31-May-2023. Patients who are in treatment suspension (due to prior undetectable PSA at study Week 36) will continue to have their PSA values, done at the local lab, evaluated by the investigator every 3 months for possible treatment reinitiation per protocol criteria. For details, refer to [Table 16](#).

Patients who discontinue study treatment or withdraw consent for further treatment will continue safety follow-up and long-term follow-up assessments per protocol (see [Section 18.8](#)). Long-term follow-up data including survival status, documentation of new antineoplastic therapies for prostate cancer, skeletal-related events, and progression on first subsequent therapy (PFS2) will be collected every 12 weeks until the final OS analysis. The associated endpoints will be summarized descriptively at the time of the final OS analysis.

Patients who receive any treatment other than their assigned study treatment for prostate cancer after unblinding will not be eligible for this OL period. All patients who permanently discontinue study drug treatment will remain in the study, complete safety follow-up, and subsequently commence long-term follow-up.

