3.5. Safety Endpoints

Safety will be assessed through adverse event (AE) reporting, laboratory and vital sign assessments. AEs will be graded by the investigator according to the Common Terminology Criteria for Adverse Events (CTCAE) version 4.03 and coded using the Medical Dictionary for Regulatory Activities (MedDRA) version in use at the time of database release.

Safety endpoints will be summarized based on the on-treatment period, modified treatment period, or re-initiation treatment period as specified.

On-Treatment Period

The on-treatment period is defined as the time from the date of first dose of study treatment through a minimum of 30 days after last dose of study treatment, or the start day of new antineoplastic drug therapy -1 day, where the last dose of study treatment is the final dose after any suspension period due to undetectable PSA. Adverse events occurring on the same day as the first dose of study treatment will be considered to have occurred during the on-treatment period. All other assessments which occur on the same day as the first dose of study treatment will be considered baseline assessments (see Section 3.5).

Safety data collected outside the on-treatment period as described above will be listed but not summarized.

Modified Treatment Period

For patients whose treatment is suspended due to undetectable PSA at week 36 the modified period is defined as the period of time of study drug exposure starting from the date of the first dose of study drug through 30 days after last dose prior to the treatment suspension PLUS the time period starting from date of first dose at study drug reinitiation through a minimum of 30 days after last dose of study treatment, or the start day of new antineoplastic drug therapy -1 day. If date of first dose at study drug reinitiation is earlier than 30 days after last dose prior to the treatment suspension, then the modified treatment period is the same as that on-treatment period.

For all other patients the modified treatment period is the same as the on-treatment period.

Reinitiation Treatment Period

The reinitiation treatment period is defined only for patients who suspend treatment due to undetectable PSA at week 36 and subsequently reinitiate treatment and is defined as the time

period starting from date of first dose at study drug reinitiation through minimum 30 days after last dose of study treatment, or start day of new antineoplastic drug therapy -1 day.

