6.8. Safety Summaries and Analyses

All patients in the safety population will be used in the safety analyses. Safety analyses will be summarized by treatment group.

The on-treatment period will be defined as in Section 5.2.5. For incomplete date of last dose of study drug and incomplete start date of the first new antineoplastic treatment that are missing the day of the month, please refer to the missing data Section 5.3.1.

At the time of analyses after protocol amendment #5, safety data for the patients treated in protocol defined open-label (OL) stage will be summarized by double blinded stage and OL stage separately.

At the time of analyses after protocol amendment #5, based on the protocol defined data collection, safety will be evaluated by the frequency of serious adverse events, frequency and severity of adverse events, frequency of study drug discontinuation due to adverse events, and frequency of new clinically significant changes in clinical laboratory values and vital signs.

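### In the open-label stage the control arm's adverse-event window hangs on a 12-weekly injection date, so it can close up to 84 days earlier than in the daily-capsule arms

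*SAP*

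**What the plan says.** SAP 3.4.1 fixes the anchor: in the leuprolide-containing arms the last-dose date "is the latest date of non-zero dosing for each of the study drugs". The drugs it names for these arms are enzalutamide or placebo, and leuprolide, so the control arm is included. In the monotherapy arm the date "is the latest date of non-zero dosing of enzalutamide".

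SAP 3.5 runs the on-treatment period "through a minimum of 30 days after last dose of study treatment, or the start day of new antineoplastic drug therapy -1 day". It adds: "Safety data collected outside the on-treatment period as described above will be listed but not summarized". The modified and reinitiation periods end on the same anchor.

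Protocol 6.3.3 states the cover of the depot: "Three injections will provide 36 weeks of treatment". Protocol 18.4.2 keeps the 12-week interval in the open-label stage, and Protocol 18.4.1 keeps enzalutamide once daily. Protocol 18.1 changes the control arm: "Patients assigned to the placebo plus leuprolide arm will no longer take the placebo capsules".

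SAP 6.8 says that safety data for men treated in the open-label stage "will be summarized by double blinded stage and OL stage separately", with safety analyses presented by treatment group. It defines no separate open-label window. It refers to Section 5.2.5 for the on-treatment definition, which is actually in Section 3.5.

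**The concern.** While every arm took daily capsules, the calendar date of the last dose was close to the date of stopping in all three arms, and the 30-day rule was roughly even. Without placebo, a control man's only dosing dates are 84 days apart. His window can close while he is still on schedule and covered by the injection. Protocol Table 16 has adverse events reviewed at each 12-weekly visit, so an event on day 60 of the cycle would be collected at the next visit and then appear only in a listing. If that event made him stop, it would be missing from the table of TEAEs leading to leuprolide discontinuation (SAP 6.8.1).

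The excluded days are those just before stopping, when events that cause discontinuation are likely to cluster. The control arm's crude open-label event percentages would be understated, and enzalutamide would look relatively worse.

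**Working it through.** **Inputs.** Last-dose rule: SAP 3.4.1. Window of 30 days, cut at the day before new antineoplastic therapy: SAP 3.5. Depot cover: Protocol 6.3.3. Open-label dosing intervals: Protocol 18.4.1 and 18.4.2. Visit window of ±5 days: Protocol Table 16. I read the 30 days as the end point and take the earlier of it and the new-therapy cut.

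**The plan's own figure.** 3 injections × 12 weeks = 36 weeks, which agrees with Protocol 6.3.3. Per injection: 36 × 7 / 3 = 84 days.

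**Loss at permanent discontinuation.** Put the last injection at day 0 and the stop at day t.

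- Control window ends at day 30.
- Capsule-arm window ends at day t + 30.
- Difference = (t + 30) − 30 = t.
- Days before the stop that are not counted = max(0, t − 30).

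| t | Control end | Capsule end | Difference | Uncounted before stop |
|---|---|---|---|---|
| 0 | 30 | 30 | 0 | 0 |
| 42 | 30 | 72 | 42 | 12 |
| 83 | 30 | 113 | 83 | 53 |
| 84 | 30 | 114 | 84 | 54 |
| 89 | 30 | 119 | 89 | 59 |

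The row t = 84 is a man who stops at the visit where the next injection was due and was not given. Days 31 to 84, that is 54 of 84 days (64%), precede his stop; the other 30 are the post-treatment tail. The row t = 89 uses the +5-day visit window.

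**Average.** If t is uniform over 0 to 84 (assumption), the mean difference is 84 / 2 = 42 days. The mean number of uncounted days before the stop is (1 + 2 + … + 54) / 85 = 1485 / 85 = 17.5.

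**Effect of new therapy.** If it starts g days after a day-84 stop, the capsule window ends at min(114, 84 + g − 1).

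- g = 1: 84 − 30 = 54 days lost.
- g = 14: 97 − 30 = 67.
- g = 30: 113 − 30 = 83.

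**Men still on treatment at cutoff.** SAP 5.3.1.1 substitutes the cutoff date only when the last dose date is completely missing (and there is no end-of-treatment page or death date). If the cutoff is used, the loss is 0. If the recorded last injection date is used, the window closes at day 30 and up to 84 − 30 = 54 days before the cutoff are lost.

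**Check of the proposed rule.** Control end = min(83, t) + 30. For t ≤ 83 this is t + 30, equal to the capsule arms. At t = 84 it is 113 against 114, a difference of 1 day.

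**The case against.** Several points can be made against this, and some of them stand.

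- *The 30 days are worded as a minimum, so the window need not close there.* True, but the SAP gives no other end date, and a programmer will use 30.
- *Protocol 10.5 and 8.5.5.2 tie the 30 days to permanent treatment discontinuation.* If that means the day a man stops, the loss is zero. But SAP 3.4.1 uses the last dosing date, so the passages conflict. Protocol 5.3 and 18.7 define permanent discontinuation as cessation of administration, which does not settle which date applies.
- *SAP 6.8 says analyses after protocol amendment #5 follow the protocol's data collection and speaks of adverse events, not TEAEs.* The same section also refers to the on-treatment definition, so it is unclear which rule governs.
- *Time-adjusted rates divide by treatment-emergent surveillance time (SAP 6.8.1).* This stands: events and person-time shrink together, so these rates are partly protected.
- *The bias runs against enzalutamide and the tables are descriptive.* This also stands, and it limits the consequence.

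A reader might infer that a control man's discontinuation event vanishes from the safety report. The documents do not support that. He is still counted under reasons for discontinuation (SAP 6.7.2), the event is still listed, and all deaths are tabulated (SAP 6.8.2). What changes is the TEAE tables and the count of deaths within 30 days of last dose.

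**Conclusion.** Followed as written, the SAP gives unequal adverse-event windows in the separately reported open-label stage. The shortfall for a control man is 0 to 84 days on the nominal schedule, once, at permanent discontinuation. It averages 42 days if stops are uniform over the interval, and is smaller if new antineoplastic therapy starts soon after.

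Three stronger readings should be resisted.

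- Every control man loses 84 days. That is the maximum, reached only by stopping at a visit where the due injection is not given. A man injected and then stopped soon afterwards loses only the days since that injection.
- Men still on treatment at the cutoff are safe. SAP 5.3.1.1 does not assure this; up to 54 days are at risk.
- The trial's conclusions are affected. No efficacy analysis uses this window.

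The documents do not say how many control men enter or discontinue in the open-label stage, so the effect on any reported percentage cannot be calculated. The point is worth correcting before the final overall survival safety tables.

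**What to change.** For the open-label safety windows in SAP 3.5 (on-treatment, modified and reinitiation):

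1. Define the end of leuprolide dosing as the earlier of injection date + 83 days and the date of the decision to discontinue permanently, or the data cutoff if the man is ongoing. The decision date must not be the last-administration date, which would return the injection date and change nothing. Check what the end-of-treatment date on the CRF records before using it.
2. Take the later of this date and the last capsule date, then add 30 days, keeping the new-therapy cut.
3. State the 30 days as an end point, and correct the reference in SAP 6.8 to Section 3.5.

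This brings the SAP into line with the permanent-discontinuation wording in Protocol 10.5 and 8.5.5.2. Apply the same anchor to deaths within 30 days of last dose in the open-label tables.

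Leave the durations in SAP 5.2.5 alone. SAP 6.7.4 divides the cumulative enzalutamide dose by the modified treatment duration, so depot cover carried into those durations would distort enzalutamide exposure and average daily dose.

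The cost is a short SAP clarification and one derivation. Some open-label TEAE counts will differ from those under the current definition. Part of the 30-day tail may not be recoverable, because Protocol Table 16 ties collection to safety follow-up, or to 30 days after the last dose if there is none; a SAP change cannot restore events that were never collected.
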